# Multimodal Group (M) – screening strategy:

The multimodal strategy uses serum CA125 interpreted using the 'Risk of Ovarian Cancer' algorithm as the primary screening modality with TVS as the second line test. The algorithms are derived from data collected in the numerous large prospective OCS studies undertaken in the 90s. The first ROC determination is based upon a single measurement of CA125 and the woman's age specific incidence of ovarian cancer. Subsequent ROC determinations are based upon both the absolute CA125 level and the

rate of change in CA125 levels. The ROC summarises, in one number, the information about risk of ovarian cancer, thus simplifying the practical implementation of the screening protocol. It is anticipated that ongoing refinement of the screening algorithms will occur in the future in a manner analogous to refinement of the screening algorithms for Downs syndrome, cervical cancer and breast cancer.

Level I screen: This involves venepuncture and serum CA125 measurement. The assay results are directly uploaded into the TMS which calculates the Risk of Ovarian Cancer (ROC). Based on the ROC value women are triaged into three risk groups (Figure 2). which are managed as follows:

- (1) Normal ROC (<1 in 3500): Volunteer returned to annual screening with the next blood test (Level I) on the one year anniversary of the randomisation date.
- (2) Intermediate ROC (<1 in 1000 and ≥1 in 3500): Volunteer recalled for a repeat CA125 measurement in 12 weeks. The ROC is recalculated with management determined as for the initial ROC. Volunteers whose ROC remain intermediate after a total of three CA125 tests are referred for a Level II screen (see below).
- (3) Elevated ROC (≥1 in 1000): Women were recalled for a Level II screen in 6-8 weeks with earlier screens arranged where there is a high index of suspicion.

[figure not shown]
Level II screen: This involved venepuncture for repeat CA125 assay and a TVS. Depending on the results of the Level II screen, there are three possible courses of action:

(1) Scan normal and the ROC normal or intermediate: Volunteer returned to annual screening with the next blood test (Level I) on the one year anniversary of the randomisation date.

- (2) Scan normal and the ROC elevated OR scan unsatisfactory irrespective of ROC: Repeat Level II screen in 12 weeks with earlier screens arranged where there is a high index of suspicion.
- (3) Scan abnormal irrespective of the ROC: Referral for clinical assessment with a view to surgery.

[figure not shown]
Women who have the Level II screen repeated are again triaged based on the findings to annual screening or clinical assessment.

Figure 2: Multimodal screening algorithm (updated 2009)

[figure not shown]

**High alert:** Women who on repeat level II screen have either an unsatisfactory or a normal scan with intermediate or elevated CA125 undergo a further 'high alert' CA125 in 6 weeks. This is automatically generated and once performed, by the TMS. There are three possible courses of action as depicted below:

- a) If ROC is <0.2%, the women are returned to annual screening by the TMS.
- b) if the ROC is >0.2 and <10%, a repeat level II scan and CA125 is actioned in 8 weeks time. Each case is discussed with the PIs.
- c) If ROC is >10%, a CT scan of chest and abdomen and a mammogram are performed. If appropriate, hysteroscopy is recommended. The results should be discussed with the PIs and prompt surgery needs to be undertaken.

Severe ROC and/or abnormal scan: Women whose scan is unsatisfactory or normal with a corresponding ROC>20% or an abnormal scan with a ROC normal, intermediate, elevated or severe a letter is generated at the CC, which is sent to the Lead, Nurse and GP (via Nurse) to highlight the urgency of the results. The volunteer then undergoes a Gynae outpatient department review and is to have CT chest/abdomen/pelvis, mammogram, hysteroscopy if appropriate, the results of which need to be reviewed by Pls and prompt surgery needs to be performed.

# *Ultrasound Group (U) – screening strategy:*

The ultrasound strategy uses transvaginal ultrasound (TVS) as a first line test with repeat screening after 6-8 weeks if an abnormality is detected on initial testing.

Level I screen: Women randomised to the U group will have an annual TVS at their TC. Depending on the results of the scan, there will be three possible courses of action (Figure 3):

- (1) Normal scan: Routine screening with an annual TVS (Level I) on the next anniversary (one year) of the randomisation date.
- (2) Unsatisfactory scan: A repeat Level I scan in 12 weeks.
- (3) Abnormal scan: Level II scan in 6-8 weeks. Earlier scans will be arranged where there is a high index of suspicion.

[figure not shown]
Level II screen: Depending on the results of the Level II screen, there will again be three possible courses of action:

- (1) Normal Scan: Routine screening with an annual TVS (Level I) on the next anniversary (one year) of the randomisation date.
- (2) Unsatisfactory scan: Repeat Level II screen in 6-8 weeks with earlier screens arranged where there is a high index of suspicion.
- (3) Abnormal scan: Referral for clinical assessment.

Women who have repeat Level II screens will be triaged based on their findings to annual screening or clinical assessment.

The ultrasound screening procedures are described in greater detail in a separate document (the Ultrasound Screening Protocol).

Figure 3: UKCTOCS ultrasound algorithm

## **Counselling and support**

All women on the trial will be given a leaflet explaining the trial design and objectives prior to recruitment. Staff with a detailed understanding of the study will be available at designated times at all TCs to answer volunteers' queries. All volunteers attending for a level II screen will be seen afterwards or contacted by a member of the local team who will explain the results of the scan and inform them of the timing and nature of expected follow-up. Pilot studies have suggested that a positive screen would be expected to have a positive predictive value for ovarian cancer of approximately 20-25% in the multimodal group and 5-10% in the ultrasound group.

# Clinical assessment and further investigation:

Where the protocol requires clinical assessment, the TC refers the woman to a designated NHS clinician who carries out a clinical evaluation (history and physical examination) and arranges for further investigations as appropriate. These may include:

- (1) Serum CA125 and/or other markers
- (2) Repeat Ultrasound and Doppler with a senior consultant radiologist with a specialist interest in gynaecological oncology.
- (3) CT / MRI of abdomen and pelvis.
- (4) Serum FSH / oestradiol if multiple cysts present and hysterectomy has been performed in the past to establish if patient could be still ovulating.
- (5) Mammogram to rule out breast cancer if CA125 profile is abnormal and no ovarian abnormality is detected on TVS.

In the M group, clinical assessment will include ruling out other causes of CA125 elevation (Appendix T). In the ultrasound group, some features of adnexal masses are associated with lower risk of OC and may be managed conservatively if the patient is asymptomatic and other clinical findings are not suggestive of malignancy. In women who have previously undergone a hysterectomy, there is an increased incidence of adhesions and peritoneal pseudocysts which maybe reported as 'multilocular adnexal cysts'. In addition, significant co-morbidity and the views of the individual will be taken into consideration while making a final management plan

If there is a high index of suspicion, women undergo surgery. If the risk of a cancer is considered to be low or if the patient declines surgery, then conservative management with follow up is arranged.

# Surgery:

The nature and timing of surgical intervention is decided at the consultation between the participant and the gynaecological oncologist / gynaecologist receiving the referral. Patients undergo routine investigations that are deemed appropriate for assessment of fitness for surgery. Some centres may use pre-operative assessment scoring systems to assess possible morbidity. It is to be noted that in the ultrasound group, a higher proportion of women who have had previous hysterectomy and/or endometriosis will be referred for surgery. The guidelines below represent appropriate management in the majority of cases. However, it is acknowledged that there will be circumstances where they cannot be adhered to and in such situations, management will depend upon the judgement of the clinician involved.

The primary aim of surgery will be to remove both ovaries and tubes for histopathological examination. However, there will be exceptions based on clinical grounds. One such occasion is where there are dense pelvic adhesions with increased risk of significant morbidity if dissection is undertaken. The clinician may opt to only remove the ovary found to have an abnormality on ultrasound and not dissect the contralateral 'normal looking' ovary. Hysterectomy adds to morbidity and will be avoided unless there are clear clinical indications. 'Normal looking' ovaries will be removed if associated with rising CA125 levels as malignancy has been detected in such ovaries in the pilot trial (unpublished data).

The approach to surgery will depend on the results of the pre-operative investigations and local surgical expertise. The primary intervention in most cases will be laparoscopy with the intention of performing a laparoscopic bilateral salpingo-oophorectomy. If clinical findings at laparoscopy are suggestive of ovarian cancer, or if laparoscopy is inappropriate because of technical difficulties, a laparotomy will be undertaken.

Laparoscopy - The procedure will be carried out using the surgeon's preferred technique. A thorough inspection of the whole of the abdominal cavity will be performed before aspirating any free fluid that is present and/or taking peritoneal washings. A bilateral salpingo-oophorectomy will be performed if technically possible and there are no features suggestive of ovarian cancer. Care will be taken to ensure removal of the entire ovary on each side. Aspiration of ovarian cysts will be avoided since a stage IA cancer may unwittingly be converted to a stage IC. When a histopathological diagnosis of ovarian cancer is made following a laparoscopic bilateral salpingo-oophorectomy, a formal staging laparotomy will be performed.

Laparotomy - If there is a clinical suspicion of ovarian cancer, the surgeon will carry out the laparotomy according to their usual practice in order to stage the disease and remove all macroscopic disease where possible. In addition, the clinician may decide to perform a laparotomy for bilateral salpingo-oopherectomy if this is deemed to be the best option for the individual based on clinical assessment.

#### Conservative management:

If the decision following clinical assessment, investigation and discussion with the woman is to manage the abnormality conservatively, then a follow up plan will be drawn up and the CC informed. Most women will be followed up by a repeat TVS and possibly a serum CA125 assessment in three months and returned to annual screening if the findings are unchanged at review. Women will be advised to contact their GP if they have any symptoms as would happen in normal circumstances. At subsequent annual screens, no action will be taken if there is no change in the size or character of the previously detected adnexal lesion and it remains asymptomatic.

# **Management of Incidental findings**

Ultrasound scans will sometimes reveal possible abnormalities that are outside the scope of this study. Any significant finding must be discussed with the lead researcher or other designated person. Each centre should draw up local guidelines for management of these findings. The most frequent example of this is a thickened endometrium. Women with endometrial thickness of >5mms are questioned for irregular bleeding. Suggested guidelines are that women should be referred if the endometrial thickness is > 10mms or endometrial thickness is >5 - <10 mms AND there is focal or cystic thickening or irregular bleeding. Volunteers with incidental findings will be referred to their general practitioner for further management.

# Follow up

There will be two methods of follow up

#### Postal Questionnaires

All volunteers will be sent a postal questionnaire 3.5 years from the randomisation date and in 2014 following the planned 3-year follow-up phase of the trial post end of screening.

The first and second follow-up questionnaires (Appendices N and V) will ask for details of any hospital admission or serious illness since registration with the trial. Attempts will be made to contact volunteers who do not respond by sending further questionnaires by first class post. Where necessary further efforts to contact volunteers will be made by telephone or via the general practitioner.

It is possible that women in the control group will undergo screening elsewhere. The follow up questionnaires (Appendices N and V) will ask volunteers if they have undergone ovarian cancer screening of any kind in order to document the size of this problem. In addition, the method of diagnosis of ovarian cancer amongst women in the control group will be reviewed to establish whether any cases of OC were detected by screening.

The follow up questionnaires of women in the screen and control groups of the trial will be used to document gynaecological surgical procedures undertaken following clinical presentation (i.e. not to investigate screening results). Further details of these procedures will be obtained where possible from the appropriate hospital. It will then be possible to compare the number of surgical procedures and the frequency of surgical morbidity and mortality in the screened population and the control population.

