# 1. Identification of potential ovarian/tubal cancer by coordinating centre

The Coordinating Centre (CC) is notified of new cases of ovarian/fallopian tube cancer (OC) and possible ovarian cancer by various sources.

The RC notifies the CC of all new cases of screen detected OC (and possible OC) and forwards relevant medical notes to the UKCTOCS senior research nurse or designated research associate. The RC will sometimes also notify the CC of screen negative and control arm cases where these cases are known to them. However, these volunteers do not always receive treatment at the RC hospital and will therefore not be identified through this method.

The Health &Social Care Information Centre (formerly NHS IC and prior to this, ONS) cancer registration and Death Certificates are two of the most important sources of information. Quarterly HSCIC updates are received electronically. After each\_update, a query is run to identify potential new cases of ovarian/tubal cancer. The query flags up a list of ICD-10 codes that could be related to a diagnosis of ovarian or tubal cancer (see Appendix S-III Table1)).

The cohort has also been linked to the Hospital Episode Statistics (HES) in England. HES is a comprehensive dataset of volunteers' in- and out- patient hospital admissions and corresponding disease codes from 2001-2009 and 2003-2009, respectively. HES data on the women was received by the CC in 2010. The clinical diagnosis fields of the HES dataset are searched for the ICD-10 diagnosis codes, (see Appendix S-III) and in addition, for operative procedures.

New cases can also be identified through the follow-up questionnaires, which are sent to all volunteers in both the screening and control arms. The first questionnaires were sent out at approximately 3.5 years post randomisation to the trial and the second follow-up questionnaire in 2014. A query is run, after each upload of data from returned questionnaires, to capture new cases of OC and possible OC.

The research associate may also identify cases of ovarian cancer when querying volunteers, who have been withdrawn from the trial because their ovaries have been removed. In all instances where the CC is aware that the woman has had her ovaries removed surgically, a letter and a single page questionnaire are sent to the volunteer

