**Figure 4: Outcome Review Process** 

# Morbidity and serious adverse reactions

RC: HSCIC Registration

A copy of the operative and other relevant pages of the hospital notes of women who undergo trial surgery will be obtained. A senior trial gynaecological oncologist blinded to

the randomisation group will confirm all surgical complications. Suspected unexpected serious adverse reactions will be reported within 7 days using a defined protocol and specific form (Appendix U). Complications related to screening and resulting from trial surgery will be presented regularly to the Data Monitoring and Ethics Committee.

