#### Questions about your outlook on life

1. The future seems to me to be hopeful, a

☐ Absolutely agree

☐ Somewhat agree

	ind i believe that the	nings are changing i	for the better
= 1105014tely agree = 50me what agree	□ Cannot say		
	·		gree = 1 rosoratery disag
2. I feel that it is possible to reach the goal			
☐ Absolutely agree ☐ Somewhat agree	☐ Cannot say	☐ Somewhat disa	gree ☐ Absolutely disag
Questions about your Health			
Do you have/are you being treated for an	y of the followin	g conditions (multi	iple boxes can be crossed)
☐ High blood pressure	☐ Diabetes		☐ Stroke
☐ Heart disease e.g. heart attack, angina	☐ Rheumato	oid arthritis	☐ Osteoporosis
☐ High blood cholesterol	☐ Osteoarth	ritis	
☐ I have not been treated for any of the abo	ve conditions		
Since joining UKCTOCS have you had a	ny of the followi	ng operations?	☐ Yes ☐ No
If "yes" please enter the details (multiple part of the trial)	e boxes can be fi	illed; please fill ev	en if you had them as
Operation to look at your ovaries -either	by incision or ke	eyhole (laparoscop	y )
Year of operation:	Hospital l	No.:	
Hospital at which operation took place:			
Name of Consultant:			
Hysterectomy / Removal of womb  Year of operation:  Hospital at which operation took place:	-		
Name of Consultant:			
Removal of ovaries (please tick one box)	☐ Right Ovar	y 🗆 Left Ovary	☐ Both ovaries
Year of operation:	Hospital 1	No.:	
Hospital at which operation took place: _			
Name of Consultant:			
Hysteroscopy / D&C / Scrape of your wo	omb / Operation t	to look at your woi	nb
Year of operation:	Hospital l	No.:	
Hospital at which operation took place:			
Name of Consultant:			
Name of Consultant:  Were there any complications resulting fr	om any of the ab	ove procedures?	☐ Yes ☐ No

Year of operation:	-	:
Hospital at which operation took p		
Name of Consultant:		
Any other operation of any kind. Pl	ease describe:	
ince joining UKCTOCS have you becomes(s)	en diagnosed with any cance	er? Please tell us about this(e
☐ Ovarian cancer	☐ Bowel/colorectal cancer	☐ Lung cancer
☐ Breast cancer	☐ Gastric/stomach cancer	☐ Vulval/vaginal cancer
☐ Cervical cancer	☐ Pancreatic cancer	☐ BCC/rodent/skin cancer
☐ Endometrial/uterus/womb cancer	•	☐ Other cancer
☐ I have not been diagnosed with any	y cancers	
Type of cancer:		
Year of operation:		
Hospital at which operation took pla	ace:	
Name of Consultant:		
Type of cancer:		
Year of operation:	Hospital No.:	

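### The comparison of surgical procedures, morbidity and mortality between screened and control women rests on unequal ascertainment, which is likely to inflate the procedure ratio and especially relative operative mortality under screening

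*Protocol*

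**What the plan says.** The Protocol describes two routes by which surgery becomes known.

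- **Clinically presenting surgery, screen and control groups alike.** Under Postal Questionnaires, the follow-up forms "will be used to document gynaecological surgical procedures undertaken following clinical presentation (i.e. not to investigate screening results"). On timing: "All volunteers will be sent a postal questionnaire 3.5 years from the randomisation date and in 2014". On verification: "Further details of these procedures will be obtained where possible from the appropriate hospital".
- **Trial surgery, possible only in M and U.** Under Morbidity and serious adverse reactions: "A copy of the operative and other relevant pages of the hospital notes of women who undergo trial surgery will be obtained". The same paragraph adds that a senior gynaecological oncologist blinded to "the randomisation group will confirm all surgical complications". The appended surgery forms record complications, readmissions and further operations.

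The Postal Questionnaires section then draws the conclusion at issue: "It will then be possible to compare the number of surgical procedures and the frequency of surgical morbidity and mortality in the screened population" and in the controls.

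The Protocol holds three other sources. Deaths are flagged in every arm (Cancer Registry). Known removals of ovaries are followed up with the woman and her consultant. HES in England has been linked and searched for operative procedures; of that linkage the Protocol says "HES data on the women was received by the CC in 2010". The last two appear in the section on identifying ovarian and tubal cancers. None of the three is assigned to the surgical comparison.

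**The concern.** Physical morbidity from surgery attributable to screening is secondary objective 2, and it is a large part of the harm to be set against any mortality benefit. A comparison of screened with control women answers that question only if an operation, a complication or an operative death has the same chance of being counted in each arm. Here the chance depends on the route to surgery, and one route exists only in the screened arms. Part of any observed contrast may therefore reflect how surgery was found rather than how much occurred or how safe it was.

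Operative death is the weakest point, because the woman concerned cannot return a later form.

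**Working it through.** The Protocol gives no rate of surgery, complications, operative death or questionnaire capture. There is no stated figure to reproduce, and every rate below is an assumption chosen to show direction.

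**1. The two routes side by side**

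| | Trial surgery (M, U only) | Clinically presenting surgery (all arms) |
|---|---|---|
| Operation found by | trial referral and surgery form | self-report at 3.5 years and in 2014 |
| Detail | hospital notes obtained | hospital details where possible |
| Complications | dedicated form, specialist confirmation | one yes/no item in the first questionnaire ("Were there any complications resulting" …); none in the surgery section of the second, as shown |
| Death | notes and adverse reaction form | not reportable by the woman; flagging gives the death but is not tied to an operation |

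Women were randomised from 2001 to 2005, so the 3.5-year form fell at about 2004/5 to 2009. The gap to the 2014 form is then roughly 5 to 9 years.

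**2. Number of procedures, equal capture in all arms**

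Let c be the clinical surgery rate in controls, kc that rate in screened women, t the trial surgery rate (fully captured) and s the share of clinical surgery captured.

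- True difference: t + (k − 1)c. Observed: t + s(k − 1)c.
- True ratio: k + t/c. Observed: k + t/(sc). This exceeds the true ratio whenever s is below 1.

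Take c = 20 and t = 10 per 1,000 women:

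| k | True difference | Observed, s = 0.9 to 0.5 | True ratio | Observed, s = 0.9 to 0.5 |
|---|---|---|---|---|
| 0.8 | 6.0 | 6.4 to 8.0 | 1.30 | 1.36 to 1.80 |
| 1.0 | 10.0 | 10.0 to 10.0 | 1.50 | 1.56 to 2.00 |
| 1.1 | 12.0 | 11.8 to 11.0 | 1.60 | 1.66 to 2.10 |

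The ratio is inflated in every row. The absolute excess is overstated, exact or understated according to k.

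**3. Number of procedures, unequal capture**

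Keep k = 1 and c and t as above, with a true excess of 10. If 90% of clinical surgery is captured in screened women and 70% in controls, the observed excess is (10 + 18) − 14 = 14. With the shares reversed it is (10 + 14) − 18 = 6. The first pattern is the more plausible: screened women attend every year, the scan form asks about hysterectomy and previous oophorectomy, and the surgery form has codes for unrelated and false-negative indications.

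**4. Complications per operation**

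Assume a true risk of 4% by either route. Let s1 and s0 be the capture shares of complicated and uncomplicated clinical operations. The observed clinical risk is 0.04·s1 / (0.04·s1 + 0.96·s0).

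- s1 = 0.6, s0 = 0.8: 0.024/0.792 = 3.03%; trial-to-clinical ratio 1.32.
- s1 = s0 = 0.8: 4.00%; ratio 1.00.
- s1 = 0.9, s0 = 0.8: 0.036/0.804 = 4.48%; ratio 0.89.

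The direction depends on whether a complicated operation is more or less likely to be reported.

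**5. Operative deaths**

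Let f be the share of deaths after clinical surgery that any source ties to the operation, and p the share of screened-arm operative deaths that follow trial surgery. With equal true rates per woman, the observed ratio is [p + (1 − p)f]/f = 1 + p(1 − f)/f.

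| f | p = 0.5 | p = 1 |
|---|---|---|
| 0.75 | 1.17 | 1.33 |
| 0.50 | 1.50 | 2.00 |
| 0.25 | 2.50 | 4.00 |
| 0 | undefined | undefined |

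The absolute difference in deaths per woman follows the algebra of step 2. The ratio suffers most because f can approach zero if the questionnaire is the only source.

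**The case against.** The strongest reply has four parts.

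- **Clinical surgery is found by the same questionnaires in all arms.** If it is equally frequent and equally captured, the loss cancels in the absolute excess. This stands. A reader might infer that the design necessarily overstates the harm of screening; steps 2 to 4 show that this does not follow for the excess of operations or for complications per operation.
- **Self-report is not the only source.** Non-responders are pursued, hospital details are sought, known oophorectomies are followed up, HES is searched for procedures and deaths are flagged. Both questionnaires also ask for operations done within the trial, so a like-for-like questionnaire count could be made. This stands as a description of the data held, and it rules out saying that every control operation is self-reported or that no operative death in controls can be found. It does not repair the stated comparison, which is built on questionnaires confined to clinically presenting surgery.
- **The listed secondary analysis is complication rates of trial surgery, from one source.** This stands; that analysis is untouched. The between-arm comparison is described only as possible, and a separate analysis plan could name another source.
- **The size may be exaggerated.** Capture of 70% to 85% suggests apparent ratios of 1/0.85 = 1.18 to 1/0.70 = 1.43 under equal true totals, but only if all surgery in M and U were trial surgery. If half were, the step 5 formula with s in place of f gives 1.09 to 1.21. Nor does the predictive value of 5–10% in the ultrasound group (Counselling and support) mean 9 to 19 operations without cancer per cancer found: it is stated per positive screen, and clinical assessment may lead to conservative management.

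**Conclusion.** The point holds as one of unequal ascertainment. The comparison in the Postal Questionnaires section sets well-documented trial surgery, present only in M and U, against less completely captured clinical surgery. This is likely to inflate the procedure ratio and, most of all, relative operative mortality in the screened arms. The absolute excess of procedures and the complication risk per operation could be biased either way or not at all.

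The size cannot be derived from the Protocol. The illustrations (procedure ratio 1.50 read as 1.56 to 2.00; equal operative mortality read as 1.17 to 4.00 when 75% to 25% of the relevant deaths are caught) rest wholly on assumed rates and capture shares, and on full capture of trial surgery. The ovarian cancer mortality endpoint and the complication rates of trial surgery are not affected. This is an inexpensive improvement to a secondary comparison, not a threat to the main result.

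**What to change.** For the between-arm comparison, use sources applied identically to all three arms and analyse by randomised arm:

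- gynaecological procedures and readmissions from the linked HES data for England, with the extract updated from its 2009 end to cover screening to 31 December 2011, plus enough time to include operations that follow the last screens;
- deaths within a fixed interval of such surgery, set in advance, by linking HES procedures to death flagging.

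Report the absolute excess alongside the ratio. Keep the questionnaires and trial complication forms for within-arm detail, and as supportive data for Wales and Northern Ireland. Amend the Postal Questionnaires section so that it no longer presents the questionnaires as the basis for this comparison.

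The cost is one updated extract and its analysis; the linkage and flagging already exist. The price is England-only coverage and coarser coding of complications than the trial forms give.
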